19.3.3 Medical Disorder Start and Stop Dates

Incomplete dates will not be imputed. Classification of events into *concurrent medical disorders* or *past disorders* will be based on the reported on-going status.

19.3.4 Medication Start and Stop Dates

Imputation of incomplete or partially missing dates will be done in order to assigning the medication to the categories specified in chapter 9. No duration will be calculated for medications with imputed start-or stop date, or for on-going medications.

Incomplete or missing medication dates will be imputed according to the algorithm below. If an imputed start date after this procedure is after the end date, the start date will be set to the end date.

In general, if the medication *start* date is partially or completely missing and if the medication is on-going from the lead-in study, the start date will be imputed with the imputation value used in the lead-in study.

Otherwise, the following rules will be applied:

- *Incomplete start date where day is missing:*
 - The start date will be imputed with the latest of either the date of first IMP in the extension study or the medication start date assuming that the day is the 1st of the month.
- *Incomplete start date where month and day are missing:*
 - If the year is equal to the year of first IMP in the extension study the date will be imputed with the date of first IMP in the extension study.
 - If the year is after the year of first IMP in the extension study the date will be imputed with the medication start date assuming the month and day are January 1st.
- *Missing start date:*
 - The medication start date will be imputed with the date of first IMP in the extension study
- *Incomplete end date where day is missing:*
 - The date will be imputed with the minimum value of either the last day of the reported month and year or the end of study date.
- *Incomplete end date where month and day are missing:*
 - The date will be imputed with the minimum value of either December 31st of the reported year or the end of study date.
- *Missing end date:*
 - If the medication end date is missing and the medication is not reported as on-going, the end date will be imputed with the end of study date.

19.3.5 Adverse Event Start and Stop Dates

Imputation of partially missing dates will be done in order to classify the treatment emergent status and assigning the adverse event to a period. No duration will be calculated for adverse events with incomplete start-or stop dates, or for on-going adverse events.

Incomplete adverse start-and stop dates will be imputed before handling of incomplete dates for change in intensity or seriousness (see section 19.4.2)

Incomplete adverse event start dates will be imputed according to the algorithm below. If an imputed start date after this procedure is after the adverse event end date, the start date will be set to the end date.

In general, if the AE is on-going at Baseline and the start date is partially or completely missing, the start date will be imputed with the imputation value used in the lead-in study.

- Patients not in APTS:
 - *Incomplete start date where day is missing*
The start date will be imputed with the latest of adverse event start date

assuming the day is the 1st of the month (e.g. if year=2017, and month=MAY, the start date would assumed to be 01MAY2017), and date of Visit 2

- *Incomplete start date where month and day are missing*
The start date will be imputed with the latest of adverse event start date assuming the month and day are JAN the 1st, and date of Visit 2
- Patients in APTS:
 - *Incomplete start date where day is missing*
 - If the start year and month are before the year and month of first IMP in the Treatment Period, the date will be imputed with the latest of adverse event start date assuming the day is the 1st of the month, and Visit 2
 - If the start year and month are at or after the year and month of first IMP in the Treatment Period and at or before the last visit in the Treatment Period, the date will be imputed with the latest of adverse event start date assuming the day is the 1st of the month, and the date of first IMP in study 16159B
 - If the start year and month are after the year and month of the last visit in the Treatment Period, the date will be imputed with the latest of adverse event start date assuming the day is the 1st of the month, and the day after last visit in the Treatment Period
 - *Incomplete start date where month and day are missing*
 - If the year is before the year of first IMP, the date will be imputed with the latest of adverse event start date assuming the month and day are JAN 1st, and date of Visit 2
 - If the year is equal to the year of first IMP in the Treatment Period, the date will be imputed with the date of first IMP in study 16159B

For adverse events with incomplete end dates where the day is missing, the date will be imputed with the minimum of the last day in the reported month and year and the end of study date. If both month and day are missing for an end date, the date will be imputed with the minimum of the adverse event end date assuming month and day are Dec 31, and the end of study date.

If the day in the date of intensity-or seriousness change is incomplete the date will imputed using the same algorithm as for incomplete start dates of adverse events but where the start date of the original event (that may have been imputed) or the preceding intensity if more than one intensity change is also taken into account. Three examples to illustrate this for a patient in APTS:

- If the adverse event start date of the original event was 15MAY2017, the date of first IMP in the Treatment Period was 17MAY2017, and the incomplete date for change in intensity was MAY2017, the change in intensity date would be imputed with the latest of 01MAY2017, 15MAY2017, and 17MAY2017, i.e. 17MAY2017.
- If the adverse event start date of the original event was 15MAY2017, the date of first IMP in the Treatment Period was 02MAY2017, and the incomplete date for change in intensity was MAY2017, the change in intensity date would be imputed with the latest of 01MAY2017, 15MAY2017, and 02MAY2017, i.e. 15MAY2017.
- If the adverse event start date of the original event was 15APR2017, the date of first IMP in the Treatment Period was 13APR2017, and the incomplete date for change in intensity was MAY2017, the change in intensity date would be imputed with the latest of 01MAY2017, 15APR2017, and 13APR2017, i.e. 01MAY2017.

If an imputed start date for an intensity change is after the end date for the original event, or after a later intensity change, the date of the intensity change will be set to the end date of the original event or the date of the intensity change that comes after.

The imputed start dates will be used in the classification of adverse events as TEAEs (see section 12.1.2). TEAEs will be flagged in the data.

19.4 Data with Multiple Records

19.4.1 Dose Changes in Medication

Dose changes or change in treatment regimen in concomitant medications are recorded on multiple rows in the eCRF, with different start and stop dates. When classifying medications into categories (see chapter 9), each record is considered as a separate medication, and the same drug name can be assigned to several categories for the same patient. Within a category, multiple entries will contribute as a single count in the summaries.

19.4.2 Changes in Intensity or Seriousness of Adverse Events

Changes in adverse event intensity are included as additional rows in the ADaM data, where each change in intensity will be represented as an additional row, e.g. an adverse event that changes from mild to moderate will have one additional row, one with intensity mild and one with intensity moderate (variable ASEV). The stop date for the intensity will be the stop date for the originally recorded event for the last intensity, and for the preceding rows the stop date will be set to the date of change in intensity minus 1 or the date of change if a change occurring on the same day as the originally reported event, or if there is more than one change on a day (for handling of incomplete dates, see section 19.3.5).

If the recorded start date of a serious adverse event is after the start date of the reported adverse event, the event is considered as having changed from non-serious to serious.

Recorded seriousness for an adverse event will be the most serious (mapped to SDTM variable AESER, i.e. AESER=Y for an adverse event that change from non-serious to

serious). In ADaM data, one additional row will be added for an adverse event that change from non-serious to serious, one with seriousness non-serious and one with seriousness serious (ADaM variable ASER). The stop date for the first row (ASER=N) will be the start date of the serious adverse event minus 1, and the stop date for the second row (ASER=Y) will be the stop date for the adverse event. After having changed to serious, the adverse event is considered as serious onwards.

If an intensity and seriousness is reported on the same date, rows will be added reflecting both the change in intensity and seriousness, one for each change type. This is to keep the transparency and to keep the value of the SDTM variable FASTRESC, which is mapped to the ADaM dataset. To be able to summarize the number of adverse events without counting these events twice, a flag will be added to the data indicating which adverse events that will go into the summaries.

As an example, an adverse event originally reported as being mild and non-serious, which additionally is reported as having changed to severe and serious on the same date, will have a total of 3 rows in data. One row with intensity mild, seriousness non-serious, and ANL01FL = 'Y', one row with intensity severe, seriousness non-serious, and ANL01FL = '' (empty), and one row with intensity severe, seriousness serious, and ANL01FL = 'Y'.

Duration (days) will be calculated for each intensity/seriousness based on the intensity/seriousness start-and stop dates.

When classifying adverse events into periods, an event may be assigned to more than one period. An adverse event that changes in intensity or seriousness in a period will contribute to the count of events as a single event in the summaries.

In summaries of adverse events presented by intensity, the maximum intensity of the adverse event will be used. The maximum intensity is searched for in events with changes, as well as over repeated events based on the preferred term. Adverse events for which information on intensity is missing will be classified as *severe*.

Adverse events for which information on seriousness is missing will be classified as *serious*.

References

1. United States Food and Drug Administration (US FDA). Guidance for Industry: Drug-induced liver injury: premarketing clinical evaluation. July 2009.
4. Guy W, editor. *Clinical Global Impressions*. In: Guy W, editor. *ECDEU Assessment Manual for Psychopharmacology*. Revised ed. Rockville, MD: National Institute of Mental Health; 1976; 217-222.
5. Morosini P-L, Magliano L, Brambilla L et al. Development, reliability and acceptability of a new version of the DSM-IV Social and Occupational Functioning Assessment Scale (SOFAS) to assess routine social functioning. *Acta Psychiatrica Scandinavica* 2000; 101: 323-9

Appendix II

SAS[®] Code

SAS® Code

The code for fitting the overall models mentioned in section 11.2 is given below. The variable CHG refers to the change from baseline value, NOMWEEK refers to the week variable, COUNTRY to the country variable, USUBJID to the subject identifier variable, and BASE refers to the baseline value.

```
proc mixed data = xxx order = internal method = reml;  
  class COUNTRY NOMWEEK USUBJID;  
  model CHG = COUNTRY NOMWEEK BASE BASE * NOMWEEK / ddfm = kr;  
  repeated NOMWEEK / subject = USUBJID type = un;  
  lsmeans NOMWEEK / cl alpha = 0.05;  
quit;
```

Appendix III

PCS Criteria

PCS Criteria

Table 1 PCS Criteria for Clinical Safety Laboratory Tests

Laboratory Test	CDISC Term	Unit	PCS Low	PCS High
Haematology / Coagulation				
B-haemoglobin	HGB	g/dL	≤ 9.5 (women) ≤ 11.5 (men)	≥ 16.5 (women) ≥ 18.5 (men)
B-erythrocytes (red cell count)	RBC	x 10E12/L	≤ 3.5 (women) ≤ 3.8 (men)	≥ 6.0 (women) ≥ 7.0 (men)
B-haematocrit (packed cell volume)	HCT	V/V	≤ 0.32 (women) ≤ 0.37 (men)	≥ 0.50 (women) ≥ 0.55 (men)
B-MCV (mean cell volume)	MCV	fL	≤ 0.8 x LLN	≥ 1.2 x ULN
B-total leucocyte (white cell count)	WBC	x 10E9/L	≤ 2.8	≥ 16
B-neutrophils/leucocytes	NEUTLE	%	≤ 20	≥ 85
B-eosinophils/leucocytes	EOSLE	%		≥ 10
B-basophils/leucocytes	BASOLE	%		≥ 10
B-lymphocytes/leucocytes	LYMLE	%	≤ 10	≥ 75
B-monocytes/leucocytes	MONOLE	%		≥ 15
B-thrombocytes (platelet count)	PLAT	x 10E9/L	≤ 75	≥ 600
P-INR (prothrombin ratio)	INR	Ratio		≥ 2.0
B-prothrombin time	PT	Sec		≥ 18
Liver				
S-aspartate aminotransferase	AST	IU/L		≥ 3 × ULN
S-alanine aminotransferase	ALT	IU/L		≥ 3 × ULN
S-bilirubin	BILI	µmol/L		≥ 34
S-bilirubin, direct	BILDIR	µmol/L		≥ 12
S-bilirubin, indirect	BILIND	µmol/L		≥ 22
S-alkaline phosphatase	ALP	IU/L		≥ 3 × ULN
S-gamma glutamyl transferase	GGT	IU/L		≥ 200
S-alpha-glutathione S-transferase (alpha-GST)	GSTAL	µg/L		≥ 20
Kidney				
S-creatinine	CREAT	µmol/L		≥ 1.5 x ULN
B-urea nitrogen (BUN)	BUN	mmol/L		≥ 11
S-uric acid (urate)	URATE	µmol/L		≥ 510 (women) ≥ 630 (men)
Electrolytes				
S-sodium (natrium)	SODIUM	mmol/L	≤ 125	≥ 155
S-potassium (kalium)	K	mmol/L	≤ 3.0	≥ 6.0

Laboratory Test	CDISC Term	Unit	PCS Low	PCS High
S-calcium	CA	mmol/L	≤ 1.8	≥ 3.0
S-chloride	CL	mmol/L	≤ 90	≥ 117
S-magnesium	MG	mmol/L	≤ 0.6	≥ 1.3
S-phosphate (phosphorus, (inorganic))	PHOS	mmol/L	≤ 0.65	≥ 1.95
S-bicarbonate	BICARB	mmol/L	≤ 12	≥ 38
Endocrine / Metabolic				
B-glucose, non-fasting/unknown	GLUC	mmol/L	≤ 3.4	≥ 9.4
B-glucose, fasting	GLUC	mmol/L	≤ 3.0	≥ 6.0
S-glucose, non-fasting/unknown	GLUC	mmol/L	≤ 3.9	≥ 11.1
S-glucose, fasting	GLUC	mmol/L	≤ 3.5	≥ 7.0
B-glycosylated haemoglobin, fasting	HBA1C	%		≥ 6.5
S-prolactin	PROLCTN	mIU/L		≥ 1350
S-thyrotropin/TSH	TSH	mIU/L	≤ 0.3	≥ 5.5
S-protein (total)	PROT	g/L	≤ 45	≥ 95
S-albumin	ALB	g/L	≤ 27	
Lipids				
S-cholesterol total, non-fasting/unknown	CHOL	mmol/L		≥ 7.8
S-cholesterol total, fasting	CHOL	mmol/L		≥ 6.2
S-triglycerides, non-fasting/unknown	TRIG	mmol/L		≥ 5.65
S-triglycerides, fasting	TRIG	mmol/L		≥ 4.2
S-LDL cholesterol, non-fasting/unknown	LDL	mmol/L		≥ 5.3
S-LDL cholesterol, fasting	LDL	mmol/L		≥ 4.9
S-HDL cholesterol, non-fasting/unknown	HDL	mmol/L	≤ 0.8	
S-HDL cholesterol, fasting	HDL	mmol/L	≤ 0.9	
Cardiac/Skeletal/Muscle				
S-creatinine kinase (total)	CK	IU/L		≥ 400 (women) ≥ 750 (men)
S-creatinine kinase MB isoenzyme	CKMB	µg/L		≥ 8.5 or
	CKMBCK	%		≥ 3.5% of total CK
S-lactate dehydrogenase (total)	LDH	IU/L		≥ 750
S-troponin I	TROPONI	µg/L		≥ 1.5
S-troponin T	TROPONT	µg/L		≥ 0.4
Infection				
S-C-reactive protein	CRP	mg/L		≥ 25
S-globulin (total)	GLOBUL	g/L	≤ 15	≥ 55

Laboratory Test	CDISC Term	Unit	PCS Low	PCS High
Urine				
Urinary pH	PH		≤ 4	≥ 9

S=serum; B=whole blood; U=urine

Table 2 PCS Criteria for Vital Signs, Weight/BMI, and Waist Circumference

Variable	CDISC Term	Unit	PCS Low	PCS High
Waist circumference	WSTCIR	Cm	decrease ≥ 7%	increase ≥ 7%
Weight	WEIGHT	Kg	decrease ≥ 7%	increase ≥ 7%
Body Mass Index	BMI	kg/m ²	decrease ≥ 7%	increase ≥ 7%
Pulse rate, supine/sitting/unknown	PULSE	beats/min	< 50 and decrease ≥ 15	≥ 120 and increase ≥ 15
Diastolic blood pressure, supine/sitting/unknown	DIABP	mmHg	≤ 50 and decrease ≥ 15	≥ 105 and increase ≥ 15
Systolic blood pressure, supine/sitting/unknown	SYSBP	mmHg	≤ 90 and decrease ≥ 20	≥ 180 and increase ≥ 20
Orthostatic systolic blood pressure	OBP	mmHg	≤ -30	
Orthostatic pulse rate	OPR	beats/min		≥ 20
Temperature	TEMP	°C	decrease ≥ 2	≥ 38.3 and increase ≥ 2

Increase/decrease is relative to the baseline value.

Table 3 PCS Criteria for ECG Parameters

ECG Parameter	CDISC Term	Unit	PCS Low	PCS High
Absolute Time Interval				
PR interval	PRMEAN	Msec		≥ 260
QRS interval	QRS DUR	Msec		≥ 150
QT interval	QTMEAN	Msec		≥ 500
Derived Time Interval				
Heart rate	HRMEAN	beats/min	< 50 and decrease ≥ 15	≥ 120 and increase ≥ 15
QTcB interval	QTcB	Msec	< 300	> 500 or increase > 60
QTcF interval	QTcF	Msec	< 300	> 500 or increase > 60

Increase/decrease is relative to the baseline value.

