**Panel 4 Clinical Safety Laboratory Tests**

Haematology	Livera	Kidneya
B-haemoglobin	S-total bilirubin	S-creatinine
B-erythrocyte count	S-conjugated bilirubin	S-urea nitrogen (BUN)
B-haematocrit	S-alkaline phosphatase (AP)	S-uric acid
B-MCV	S-alanine aminotransferase (ALT)	Urine (dipstick)
B-MCHC	S-aspartate aminotransferase (AST)	U-protein (dipstick)
B-total leucocyte count	S-lactate dehydrogenase (LDH)	U-glucose (dipstick)
B-neutrophils (% of total leucocytes)	S-γ-glutamyl transferase (γGT)	U-blood (dipstick)
B-eosinophils (% of total leucocytes)	Electrolytesa	U-ketones (dipstick)
B-basophils (% of total leucocytes)	S-sodium	Urine drug screenc
B-lymphocytes (% of total leucocytes)	S-potassium	U-Amphetamine
B-monocytes (% of total leucocytes)	S-chloride	U-Barbiturates
B-thrombocyte count	S-bicarbonate	U-Benzodiazepines
P-INR (prothrombin ratio)	S-calcium (total)	U-Cannabinoids
Lipidsa	Endocrine and Metabolica	U-Cocaine
S-cholesterol (total) (fasting)	S-albumin	U-Methadone
S-triglycerides (fasting)	P-glucose (fasting)	U-Opiates
S-low density lipoprotein (LDL)	S-prolactin b	U-Phencyclidine
S-high density lipoprotein (HDL)	B-HbA1c (fasting)	Pregnancy (women only)
	S-total protein	S-hCG
		Urine dipstick d
		Additional Test
		S-Creatine phosphokinase (CPK) e

B – blood; P – plasma; S – serum; U – urine

- Clinical chemistry
- Result will remain blinded
- Urine samples will be collected and analysed at the site using dipsticks
- Can be repeated at any time during the study at the discretion of the investigator. All positive urine pregnancy test results must be confirmed by a serum test.
- S-troponin T, reflex for CPK >500U/l.

Blood samples for the clinical safety laboratory tests will be collected as outlined in [Panel 2](#). The blood sampling and handling procedures are described in the study-specific *Laboratory Specification Manual*.

The blood samples will be analysed at the central laboratory.

The investigator must review (initial and date) the results of the clinical safety laboratory tests as soon as possible after receipt of those results. Out-of-range values must be interpreted by the investigator as “not clinically significant” or “clinically significant” with a comment concerning the planned follow-up. Tests for clinically significant out-of-range values must be

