12.3 Clinical Safety Laboratory Test Data

12.3.1 Data Presentation

The PCS criteria used for the clinical safety laboratory tests are the Lundbeck standard PCS criteria described in SOP_09978: *PV – PCS and standard reference values for laboratory investigations, vital signs and ECGs in clinical studies*, version 6, and are also included in [Table 1](#).

The clinical safety laboratory test values will be presented either in conventional or Système International (SI) units.

Descriptive statistics for the laboratory parameters in the Treatment Period, both absolute values and changes from baseline, will be presented by test and week and the last assessment in the Treatment Period. The summaries for the absolute values will also include summaries for baseline.

The number and percentage of patients with at least one PCS low value or PCS high value at any post-baseline assessment in the Treatment Period will be summarized by laboratory parameter. All available assessments in the period will be included in the evaluation of PCS.

Non-fasting tests of S-Cholesterol, S-Glucose, S-HDL Cholesterol, S-LDL Cholesterol, and S-Triglycerides will be evaluated separately and only for PCS values.

Prolactin will also be presented by detailed previous treatment group, i.e. where the RIS/OLZ group is split into whether the patient received Risperidone or Olanzapine in the lead-in study as well as by sex.

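### Neutrophils are judged only as a percentage of leucocytes, so a low absolute count can breach no PCS limit while a higher one is flagged low

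*SAP*

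**What the plan says.** Protocol Panel 4 lists the neutrophil test as "B-neutrophils (% of total leucocytes"), with no absolute count. SAP Appendix III, Table 1, follows this. The row "B-neutrophils/leucocytes" is in percent, with PCS low at 20 or less and PCS high at 85 or more. The row "B-total leucocyte (white cell count") is in 10E9/L, with PCS low at 2.8 or less and PCS high at 16 or more. The other differential cells are also limited as percentages only.

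No rule joins the two rows. Under SAP 12.3.1, the number of patients with a PCS low or high value "at any post-baseline assessment in the Treatment Period will be summarized by laboratory parameter". SAP 12.2 plans listings of values, with PCS and out-of-range flags, for patients who have a post-baseline PCS value. PCS values in the safety laboratory tests are a primary endpoint (SAP 4.1, Protocol 16.1). Scheduled post-baseline samples fall at Weeks 4, 24 and 52 (Protocol Panel 2).

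**The concern.** The absolute neutrophil count is the product of two results already listed for the haematology sample. Two limits applied separately to the factors cannot order patients by the product. A patient slightly above both limits has a low product and is not counted. A patient with a high leucocyte count and a low neutrophil share has a much larger product and is counted as low.

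The safety table could then show no low-neutrophil patient although low absolute counts are in the data, and could show patients whose finding is a shift in the differential. A patient who passes both limits is also absent from the SAP 12.2 listings for these variables. With three scheduled post-baseline samples, a missed value has few chances to reappear.

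**Working it through.** **Inputs**
- Leucocytes (SAP Table 1): low at 2.8 or less, high at 16 or more, in 10E9/L.
- Neutrophils (SAP Table 1): low at 20% or less, high at 85% or more.
- Other differential cells (SAP Table 1): lymphocytes low at 10% or less and high at 75% or more; monocytes high at 15% or more; eosinophils and basophils each high at 10% or more.
- Lower limit of normal for the absolute count: not in the documents. Assumed 1.5 to 2.0 x 10E9/L.

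The plan states no absolute neutrophil figure, so there is none to reproduce.

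**Formula.** Absolute count = leucocytes x neutrophil % / 100, in 10E9/L.

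**1. Lowest count that escapes.** Both limits are passed when leucocytes exceed 2.8 and neutrophils exceed 20%. The count then exceeds 2.8 x 0.20 = 0.56.

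**2. Leucocyte range in which a given count escapes.** The lower bound is 2.8. The upper bound is count / 0.20, where the percentage reaches its limit.

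| Absolute count | Upper bound | Escapes for leucocytes |
|---|---|---|
| 0.6 | 0.6 / 0.20 = 3.0 | above 2.8, below 3.0 |
| 0.75 | 0.75 / 0.20 = 3.75 | above 2.8, below 3.75 |
| 1.0 | 1.0 / 0.20 = 5.0 | above 2.8, below 5.0 |
| 1.5 | 1.5 / 0.20 = 7.5 | above 2.8, below 7.5 |

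Examples: 2.9 x 0.21 = 0.609 and 4.0 x 0.30 = 1.2. Neither patient meets the leucocyte limit or the neutrophil limit.

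**3. Highest count flagged low with leucocytes unflagged.** Leucocytes must be below 16 and neutrophils at 20% or less, so the bound is 16 x 0.20 = 3.2. Examples at exactly 20%: 7.5 x 0.20 = 1.5; 10 x 0.20 = 2.0; 12 x 0.20 = 2.4; 15.9 x 0.20 = 3.18. All four are PCS low on the percentage row.

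**4. Do the other cells trigger a flag?** They need not. At 21% neutrophils the remaining 79% can be lymphocytes 68, monocytes 8, eosinophils 2 and basophils 1 (sum 79). At 20% the remaining 80% can be 69, 8, 2 and 1 (sum 80). None of these values reaches a limit.

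**5. Size of the inversion.** 3.2 / 0.56 = 5.7. This follows from Table 1 alone.

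**6. Are the flagged counts normal?** With an assumed lower limit of 1.5, a patient at 20% is within range once leucocytes reach 1.5 / 0.20 = 7.5. With an assumed 2.0, the figure is 2.0 / 0.20 = 10.

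**The case against.** The best case for leaving the table alone has five parts.

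*The limits are the sponsor's standard.* SAP 12.3.1 adopts them from a named procedure and applies them consistently. No two passages conflict. This stands: it is a weakness of the criteria, not an error. It does not prevent one added study-level parameter. The plan already combines results elsewhere: SAP 12.3.2 joins transaminases with bilirubin, and Table 1 judges CK-MB both in absolute terms and as a share of total CK.

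*There is another safeguard.* Protocol 9.5.2 requires the investigator to judge every out-of-range value, to repeat or follow up the clinically significant ones, and to record them as adverse events, which are themselves a primary endpoint. Both components are also summarised by week. This is a real protection. It rests on individual judgement, however, and leaves the PCS count as it is.

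*A 19% result is truly low on the row as named.* This stands. The row describes the differential, and the flag misleads only if it is read as a low absolute count.

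*The documents name no haematological signal.* The target organs in Protocol 1.1.4 do not include bone marrow, and Protocol 1.1.5.3 reports no apparent trend in laboratory parameters other than CPK in the multiple-dose study. That study dosed for 21 days, whereas this one runs for 52 weeks. The point concerns whether the measure works, not a suspected effect.

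*The extreme example is a corner case.* A reader might infer that a patient with a count near 0.6 generally goes unflagged. The documents do not support that. At leucocytes of 2.8 or less the leucocyte row flags the patient, and at 3.0 or more the percentage row does. A reader might also infer that normal counts are certainly reported as low. That needs a reference range which the documents do not contain.

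**Conclusion.** The concern holds as a statement of what the criteria allow. Any absolute count above 0.56 x 10E9/L can breach neither limit. The escape range is very narrow at 0.6 and widens with the count, to leucocytes between 2.8 and 7.5 at a count of 1.5. A count of up to about 3.2 can be flagged low with leucocytes unflagged. These bounds and the 5.7-fold inversion need nothing beyond Table 1.

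Calling the flagged counts normal rests on the assumed lower limit of 1.5 to 2.0. How many patients would be affected cannot be estimated, because the documents give no joint distribution of leucocytes and neutrophil percentage. This is a cheap improvement to a primary safety summary; it contradicts nothing in the plan and does not show that low counts would go unnoticed clinically.

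**What to change.** In SAP 12.3.1 and Table 1, add a derived parameter: absolute neutrophils = leucocytes x neutrophil % / 100, calculated only when both values come from the same sample. Summarise absolute values and changes from baseline by visit and for the last assessment.

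Add a PCS-low limit for it. The sponsor should fix the value before database lock and keep it distinct from the simple out-of-range flag, because SAP 12.2 treats PCS and out-of-reference-range values as two different things.

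Keep the percentage rows, and add a note that they describe the differential and not the absolute count. The percentage flags stay in the table, but the note and the new row let a reader interpret them.

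The cost is one derived variable and one PCS row beyond the sponsor's standard list. No new sample or laboratory test is needed.
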